4.3.1.5. Partial Renal Response (LN Cohort Only)

Partial renal response (PRR) will be assessed at Weeks 26 and 50. To achieve PRR, participants who did not achieve CRR in the LN cohort must meet all of the following criteria:

- Decrease in UPCR ≥ 50% compared to the baseline value based on mean of two 24-hour urine collections obtained within 2 weeks prior to the study visit (Week 26 or 50)
- eGFR > 60 mL/min/1.73 m² or no eGFR reduction ≥ 20% from the baseline value based on the mean of 2 values. The first eGFR value must be obtained within 2 weeks prior to the study visit (Week 26 or 50) and the second eGFR value will be obtained on the study visit (Week 26 or 50)
- No treatment failure (as defined in Section 4.3.1.10)

The percentage of participants meeting the criteria for PRR as well as individual components of PRR will be summarized at Weeks 26 and 50 by treatment group by calculating the point estimate and 2-sided 95% CI, based on exact confidence limits using the Clopper-Pearson method.

Study participants with treatment discontinuation will be treated as failure to meet PRR criteria and considered nonresponders.

A bar chart will also be provided displaying the proportion of participants meeting the criteria for PRR as well as individual components of PRR at Weeks 26 and 50 by treatment group.

4.3.1.6. Time to the First Occurrence of UPCR \leq 0.5 g/g (LN Cohort Only)

Time to the first occurrence of UPCR ≤ 0.5 g/g will be summarized by spot urine sample.

Participants will be censored at the earliest of their treatment discontinuation time, receipt of additional standard of care therapy (LN cohort only), study withdrawal or death, or at Week 50 when the event of UPCR ≤ 0.5 g/g has not yet occurred.

Kaplan-Meier will be used to estimate the survival curve. The corresponding Kaplan-Meier curve for each treatment group will be created by plotting the cumulative proportion surviving against the survival times.

The curves for the ALXN2050 180 mg and placebo treatment groups will be statistically compared with a log-rank test of the null hypothesis that there is no difference between the population survival curve over time. A corresponding summary table will present the cumulative distribution function (CDF) estimate, the number of participants at risk, the number of participants responding (ie, occurrence of UPCR \leq 0.5 g/g), and the number of participants censored at each post-Baseline time point by treatment group. The table will also present first quartile, median, and third quartile, along with corresponding 2-sided 95% CI of time to response.

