In addition to the proteinuria analyses based on 24-hour urine collections, the percentage change from baseline in spot UPCR at each scheduled visit up to Week 50 will also be analyzed using an MMRM model in a similar manner. The plot to present the trajectory of proteinuria over time based on spot UPCR will be visualized by treatment/treatment sequence group.

In addition to the MMRM analysis, observed values, change from baseline, and percent change from baseline in proteinuria will be summarized descriptively by treatment group at baseline and each post-Baseline time point separately by study phase.

The trajectory of proteinuria over time will be visually presented by plotting the mean proteinuria based on 24-hour urine collections at each time point by treatment/treatment sequence group.

4.3.1.2. Reduction in Proteinuria at Weeks 26 and 50 Compared to Baseline (Both Cohorts)

The percentage of participants achieving > 30% and > 50% reduction in proteinuria based on 24-hour urine collection at Weeks 26 and 50 will be summarized by treatment group by calculating the point estimate and 2-sided 95% CI, based on exact confidence limits using the Clopper-Pearson method.

Participants for receipt of additional standard of care therapy (LN cohort only) or treatment discontinuation will be treated as failure to meet the reduction cutoff and considered nonresponders.

A bar chart will also be provided displaying the percentage of participants achieving > 30% and > 50% reduction in proteinuria at Weeks 26 and 50 by treatment group.

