4.4.7. Time to First CRR or PRR (LN Cohort Only)

For LN cohorts, time to the first occurrence of CRR or PRR will be summarized by spot urine sample.

Participants will be censored at the earliest of their treatment discontinuation time, receipt of additional standard of care therapy, study withdrawal or death, or at Week 50 when the event of CRR or PRR has not yet occurred.

The analysis will be performed using 2 approaches:

- Time to the first CRR (using spot UPCR)
- Time to the first CRR or PRR (using spot UPCR) time to the first event (either CRR or PRR, whichever occurred first)

Kaplan-Meier will be used for estimating the survival curve. The corresponding Kaplan-Meier curve for each treatment group will be created by plotting the cumulative proportion surviving against the survival times.

The curves for the ALXN2050 180 mg and placebo treatment groups will be statistically compared with a log-rank test of the null hypothesis that there is no difference between the population survival curve over time. A corresponding summary table will present the CDF estimate, the number of participants at risk, the number of participants responding (ie, occurrence of first CRR or PRR), and the number of participants censored at each post-Baseline time point by treatment group. The table will also present first quartile, median, and third quartile, along with corresponding 2-sided 95% CI of time to response.

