4.4.8. Overall Renal Response (LN Cohort Only)

For the LN cohort, Overall Renal Response (ORR) is defined as the composite of CRR and PRR.

The percentage of participants meeting the criteria for ORR will be summarized at Weeks 26 and 50 by treatment group by calculating the point estimate and 2-sided 95% CI based on exact confidence limits using the Clopper-Pearson method.

Participants with additional standard of care therapy (LN cohort only) or treatment discontinuation will be treated as failure to meet ORR criteria and considered nonresponders.

4.4.9. Time to the First Occurrence of UPCR > 50% Decrease from Baseline (LN Cohort Only)

For the LN cohort, time to the first occurrence of UPCR > 50% decrease from baseline will be summarized by spot urine sample.

Participants will be censored at the earliest of their treatment discontinuation time, receipt of additional standard of care therapy, study withdrawal or death, or at Week 50 when the event of UPCR > 50% decrease has not yet occurred.

Kaplan-Meier will be used to estimate the survival curve. The corresponding Kaplan-Meier curve for each treatment group will be created by plotting the cumulative proportion surviving against the survival times.

The curves for the ALXN2050 180 mg and placebo treatment groups will be statistically compared with a log-rank test of the null hypothesis that there is no difference between the population survival curve over time. A corresponding summary table will present the CDF estimate, the number of participants at risk, the number of participants responding (ie, occurrence of UPCR decrease > 50%), and the number of participants censored at each post-Baseline time point by treatment group. The table will also present first quartile, median, and third quartile, along with corresponding 2-sided 95% CI of time to response.

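### In the LN cohort, the three time-to-response analyses censor at added therapy, discontinuation or death, so 1 minus Kaplan-Meier overstates response and conflicts with the binary endpoints

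*SAP*

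**What the plan says.** SAP 4.3.1.6 (secondary, LN only) measures time to the first spot UPCR of 0.5 g/g or less. Participants without the event are "censored at the earliest of their treatment discontinuation time, receipt of additional standard of care therapy (LN cohort only), study withdrawal or death", or otherwise at Week 50. The analysis follows directly: "Kaplan-Meier will be used to estimate the survival curve". The 180 mg and placebo curves are then "statistically compared with a log-rank test of the null hypothesis that there is no difference between the population survival curve over time". The accompanying table reports a CDF estimate of response and its quartiles.

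SAP 4.4.7 (time to first CRR or PRR) uses the same rule: "censored at the earliest of their treatment discontinuation time, receipt of additional standard of care therapy, study withdrawal or death, or at Week 50". SAP 4.4.9 (time to a UPCR decrease of more than 50%) does too, ending "or at Week 50 when the event of UPCR > 50% decrease has not yet occurred".

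The binary endpoints go the other way. Under SAP 4.3.1.2, participants with added therapy or treatment discontinuation "will be treated as failure to meet the reduction cutoff and considered nonresponders". For overall renal response (SAP 4.4.8), added therapy or "treatment discontinuation will be treated as failure to meet ORR criteria and considered nonresponders". CRR and PRR (SAP 4.3.1.4 and 4.3.1.5) require no treatment failure and count discontinuation as non-response.

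Protocol 9.4.6.2.2 plans the Kaplan-Meier curve and log-rank test for the secondary endpoint but gives no censoring rule, so the rule comes from the SAP. These three endpoints appear neither in SAP Table 6 nor in the dosing-pause sensitivity analyses of SAP 4.3.2.

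**The concern.** Reading 1 minus Kaplan-Meier as the probability of response assumes that a censored participant would go on to respond at the rate of those still at risk. Several triggers for added therapy make that implausible, because they select people whose proteinuria is far from the target. Removing them shrinks the risk set, and each later response then counts for more.

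Two things are at stake. First, the reported response curve and its quartiles are too favourable. Second, one participant can be a non-responder in the overall-renal-response table and, in the time-to-CRR/PRR curve, be treated as if still able to respond. The SAP does not explain the difference, and no planned analysis of these endpoints would show its effect.

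**Working it through.** **The plan's own LN figure.** The only LN design figure is power for the primary endpoint. With 30 per arm and 10% dropout, 27 remain per arm; the effect is log(0.60/0.40) = 0.405 and the SD is 0.60. Then 0.405 / (0.60 × √(2/27)) = 2.483, and 2.483 − 1.645 = 0.838, giving power of 79.9% against the stated 80% or so. It reproduces. No event count, response rate or added-therapy rate is given for the time-to-response endpoints, so all rates below are assumptions.

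**Is the censoring informative?**
- Entry requires UPCR of at least 1 g/g (Protocol 5.1.2). Suboptimal Response means a fall of 25% or less (SAP 4.3.1.11). UPCR is then at least 1 × 0.75 = 0.75 g/g, above the 0.5 g/g target and well short of a 50% fall.
- One Renal Flare criterion is a doubling from the lowest value after first dose (SAP 4.3.1.8). From a lowest value above 0.5 g/g, that means above 2 × 0.5 = 1.0 g/g.
- For SAP 4.4.7 the link is definitional if the CRR and PRR criteria carry over to the spot-UPCR version. Added therapy for a protocol-defined reason is treatment failure (SAP 4.3.1.10), and treatment failure rules out both responses.

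**Effect on one arm.** Assume 40% truly respond, spread evenly over Weeks 8, 12, 16, 20, 26, 34, 42 and 50 (5% at each). Added therapy goes only to non-responders, uniformly over Weeks 4 to 46. The fraction at risk at the k-th visit, in week v, is 1 − 0.05(k − 1) − R × (v − 4)/42, with the last fraction capped at 1. Kaplan-Meier multiplies (1 − 0.05 / at risk) over the visits.

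| Week | At risk, R = 30% | Factor | At risk, R = 10% | Factor |
|---|---|---|---|---|
| 8 | 0.971 | 0.949 | 0.990 | 0.950 |
| 12 | 0.893 | 0.944 | 0.931 | 0.946 |
| 16 | 0.814 | 0.939 | 0.871 | 0.943 |
| 20 | 0.736 | 0.932 | 0.812 | 0.938 |
| 26 | 0.643 | 0.922 | 0.748 | 0.933 |
| 34 | 0.536 | 0.907 | 0.679 | 0.926 |
| 42 | 0.429 | 0.883 | 0.610 | 0.918 |
| 50 | 0.350 | 0.857 | 0.550 | 0.909 |
| 1 − product | | 50.4% | | 42.7% |

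The truth is 40% in both columns, so the overstatement is 10.4 and 2.7 points. The false gap of 7.7 points equals about 0.077 × 30 = 2.3 participants per arm.

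**Later added therapy.** With timing uniform over Weeks 26 to 46, the same calculation gives 47.2% versus 41.7%. Spreading responses over all ten LN spot-urine visits from Week 2 gives 46.1% versus 41.4%.

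**Log-rank test.** In a simulation with 30 per arm and 6,000 replicates (true response 40% in both arms, added therapy 10% on active and 30% on placebo, Weeks 4 to 46), the nominal one-sided 5% test rejected 11.8% of the time favouring placebo and 2.0% favouring active. Keeping these participants at risk to Week 50 as non-responders gave 4.7% and 5.2%.

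**Direction.** Take constant hazards over 50 weeks, a for response and r for added therapy. Kaplan-Meier gives 1 − exp(−50a); the proportion who respond before added therapy is a/(a + r) × (1 − exp(−50(a + r))). The difference in points is:

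| KM response | 10% added therapy | 20% | 30% | 40% |
|---|---|---|---|---|
| 20% | 1.1 | 2.2 | 3.4 | 4.7 |
| 40% | 2.4 | 4.9 | 7.5 | 10.2 |
| 60% | 4.0 | 8.1 | 12.4 | 17.0 |

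The overstatement rises with added therapy and also with response. At 60% response and 10% added therapy it is 4.0 points, more than the 3.4 points at 20% and 30%. In the 30-per-arm simulation, an active arm with 50% response and 10% added therapy was overstated by 3.6 points, and a placebo arm with 30% and 15% by 3.0.

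**The case against.** A reader might infer that the arm with the most added therapy is always overstated most, that placebo is therefore flattered, and that the log-rank test is biased whenever added-therapy rates differ. The documents do not support this. They give no such rates, and the calculations show that the order can reverse. The log-rank test under the present rule is still a valid comparison of cause-specific hazards; what it does not compare is response probabilities.

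The link to proteinuria is also only partial. Severe Extrarenal SLE Flare leads to added therapy, yet its definition excludes proteinuria. Renal Flare can be met through creatinine with urinary sediment or biopsy. A flare after CRR will mostly occur in someone who has already had the event and is not censored. Added therapy for Suboptimal Response is allowed only after Week 26, which reduces the distortion. The assumption that nobody who receives added therapy would otherwise have responded is an extreme one.

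Finally, the affected analyses are one secondary and two exploratory endpoints, declared descriptive. The SAP also tabulates numbers censored, treatment-failure rates by arm and non-responder results at Weeks 26 and 50, so a careful reader could see part of the problem.

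All of this stands and limits the weight of the point. It does not rescue the CDF as a response probability, and it does not explain why the same events are handled in opposite ways.

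**Conclusion.** For these three LN endpoints the censoring is informative, and the CDF and its quartiles overstate response. That rests on the SAP's own trigger definitions and on its non-responder rule for the binary endpoints.

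The size is conditional. Under the assumed 40% response in both arms and 30% versus 10% added therapy, the overstatement is about 10 and 3 points, or roughly 6 to 7 and 1 to 2 points if added therapy comes only after Week 26. How this shifts the treatment comparison depends on response rates, added-therapy rates and timing, so no direction can be claimed in advance. The primary analysis is unaffected. It is a cheap improvement to supportive analyses.

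**What to change.** In SAP 4.3.1.6, 4.4.7 and 4.4.9:

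- Treat additional standard of care therapy, treatment discontinuation not caused by the dosing pause, and death before response as competing events.
- Report the Aalen-Johansen cumulative incidence of response and compare 180 mg with placebo by Gray's test. Alternatively, keep these participants at risk to Week 50 as non-responders and run the log-rank test on those times.
- Keep administrative censoring for stops or missing data due only to the pause of 06 Sep 2024 (SAP Section 1), whose missing outcomes SAP 4.1.4 assumes to be missing at random. Counting these stops as non-response would understate response.
- Censor study withdrawal that has no earlier competing event.
- Retain the present rule as a supplementary analysis, and state that its log-rank test compares cause-specific hazards.

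The cost is wording in three sections and some programming, with no new data. The downside is that the reported response curves will be lower.

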4.2. Scientific Rationale for Study Design

Justification for specific design elements is provided in Table 9.

Table 9: Scientific Rationale for the Design of Study ALXN2050-NEPH-201

Design Element	Rationale
Target populations	Glomerular diseases such as LN and IgAN continue to respond poorly to treatment, resulting in CKD over time. While there has been some progress in terms of approved treatments with 2 recent approvals in some countries for patients with LN (ie, belimumab and voclosporin) and IgAN (budesonide), there remains a significant unmet need for novel interventions which would allow more definitive treatments for LN as well as disease-specific treatments for patients with IgAN, particularly in patients who are at risk of progressive kidney disease. See Section 2.2.3 and Section 2.2.4.
Randomized, double-blind, placebo-controlled	A randomized, double-blind, placebo-controlled study design in addition to allowed concomitant therapy consistent with the standard of care is selected to provide the most robust evidence of the efficacy of ALXN2050 on clinical response, disease progression, and safety. Randomization minimizes the effects of baseline differences and confounding factors on the study endpoints. The use of a placebo comparator allows for the true treatment effect of ALXN2050 by minimizing the risk of selection bias.
Randomization stratum	A single randomization stratum was selected for each cohort to ensure equal distribution of baseline characteristics that may impact the endpoints. See Section 6.3.1.
Selection of 2 dose levels (ALXN2050 180 mg bid and ALXN2050 120 mg bid)	The optimal dose of ALXN2050 in glomerular diseases is not known. Thus, participants will be randomized to a high-dose group (180 mg bid), a low-dose group (120 mg bid), or a placebo group in a 3:1:3 allocation ratio. The primary analysis will compare the high-dose treatment group to the placebo treatment group. A smaller number of participants will be randomized to the low-dose treatment group to collect supportive data that will be summarized descriptively. Given the unknown degree of AP inhibition required to achieve clinical efficacy in these indications and to ensure robust AP inhibition in a majority of patients, 180 mg bid was chosen for the high-dose group. See Section 4.3.
Primary endpoint (proteinuria)	Change in proteinuria is considered a valid surrogate endpoint for kidney survival in glomerular diseases. See Section 4.2.1.

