9.4.6. Efficacy Analyses

9.4.6.1. Analyses of Primary Efficacy Endpoint

The primary analysis of the primary efficacy endpoint will be based on the Full Analysis Set (FAS).

Proteinuria will be measured and summarized by absolute protein in g/day as well as by UPCR in g/g for each disease cohort.

For the LN cohort, the primary endpoint will be measured by UPCR in g/g derived from a single 24-hour urine collection at Screening and the mean of 2 separate 24-hour urine collections at Week 26.

For the IgAN cohort, the primary endpoint will be measured by absolute protein in g/day derived from the mean of 2 valid 24-hour urine collections.

To reduce skewness, the natural logarithm will be used to transform proteinuria values before analysis. An analysis of covariance (ANCOVA) will be used for the primary efficacy endpoint to compare reductions in proteinuria between the ALXN2050 180 mg bid and placebo treatment groups. The ANCOVA model will include change from baseline in log-transformed proteinuria as the response variable and will adjust for baseline log proteinuria. Data from the ALXN2050 120 mg bid treatment group will be summarized descriptively, with no formal statistical

comparisons planned. The point estimate and 2-sided 90% confidence interval (CI) for the mean difference of log-transformed proteinuria will be back-transformed (via exponentiation) to obtain the GMR and corresponding 2-sided 90% CI. The values will then be expressed as percentage change in adjusted geometric mean of proteinuria at Week 26 relative to baseline.

For the LN cohort, data collected on or after receipt of additional standard of care therapy will be imputed using the proteinuria value from the 24-hour urine collection performed at the time of Renal Flare for the primary efficacy analysis. Additional sensitivity analyses will be performed to assess the impact of the missing data and assumptions.

The primary efficacy endpoint analysis will also be performed on the Per Protocol Set.

Full details of these analyses will be provided in the SAP.

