9.4.6.2.2. Secondary Efficacy Analyses for LN Cohort Only

The percentage of participants achieving the following secondary endpoints will be summarized by treatment group by calculating the point estimate and 2-sided 95% CI, based on exact confidence limits using the Clopper-Pearson method:

- Meeting the criteria for CRR as well as individual components of CRR at Week 26 and Week 50
- Meeting the criteria for PRR at Week 26 and Week 50
- Achieving corticosteroid taper to 7.5 mg/day at Week 12, Week 26, and Week 50
- Experience of protocol-defined Renal Flare through Week 50
- Experience of protocol-defined Extrarenal SLE Flare through Week 50
- Meeting the criteria for Treatment Failure through Week 50
- Meeting the criteria for Suboptimal Response through Week 50

Time to the first occurrence of UPCR \leq 0.5 g/g will be summarized based on spot urine samples. A Kaplan-Meier cumulative distribution curve will be generated for treatment group, and a log-rank test comparing the curves for ALXN2050 180 mg bid and placebo treatment groups will be performed. The corresponding summary table will present by treatment group the cumulative distribution function (CDF) estimate, the number of participants at risk, the number of participants responding, and the number of participants censored at each postbaseline time point. The table will also present the first quartile, median, and third quartile, along with 2-sided 95%CI, of time to UPCR \leq 0.5 g/g.

Serum albumin will be summarized at baseline and each scheduled postbaseline time point by treatment group using descriptive statistics for the observed value as well as the change from baseline.

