26-week Blinded Initial Evaluation Period. The LN cohort will continue with the same treatment allocation during the 24-week Blinded Extended Treatment Period (ALXN2050 180 mg bid, ALXN2050 120 mg bid, or placebo bid). For the IgAN cohort, participants assigned to the placebo group will also be assigned to their active study treatment for the 24-week Blinded Extended Treatment Period (ALXN2050 120 mg bid or ALXN2050 180 mg bid) in a 1:1 allocation ratio at the time of initial randomization.

The randomization stratum is defined as follows:

[figure not shown]
- LN cohort: corticosteroid induction treatment initiation (prior to Screening, during Screening Period)
- IgAN cohort: mean proteinuria from 2 valid 24-hour urine collections (1 to 2 g/day, > 2 g/day)

During the OLE Period, participants in both cohorts receiving ALXN2050 during the 24-week Blinded Extended Treatment Period will continue their active treatment at the same dose level. Once an optimal dose is identified based on results of the primary analysis at Week 26 for each cohort and/or Data Monitoring Committee review of the safety and efficacy data, all participants in that cohort with at least 50 weeks of study treatment will receive the optimal dose of ALXN2050. Participants in the LN cohort randomized to the placebo group will no longer receive placebo and will continue to receive allowed concomitant therapy alone. These participants will have the option to receive ALXN2050 180 mg bid or the optimal dose (if already identified) if the participant has a renal flare or suboptimal response.

In the LN cohort, participants who meet the criteria for protocol-defined renal flare or for extrarenal systemic lupus erythematosus (SLE) flare will receive additional standard of care therapy. After Week 26, participants may also receive additional standard of care therapy for protocol-defined suboptimal response. The specific choice of additional standard of care therapy(ies) is generally at the discretion of the Investigator.

Participants who discontinue study intervention and remain on study may receive treatment consistent with local standard practice for their disease per Investigator judgment.

[figure not shown]
Figure 1: Study Design Schematic (LN Cohort)

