4.2.2. Main Analytical Approach

An analysis of covariance (ANCOVA) will be used for the primary efficacy analysis to compare reductions in proteinuria between the ALXN2050 180 mg bid treatment and placebo groups. The ANCOVA model will include change from baseline in log-transformed proteinuria as the response variable and will adjust for baseline log proteinuria and the randomization stratification factor. The treatment effect will be evaluated using the least-squares mean difference between treatment groups. The point estimate and 2-sided 90% CI for the mean difference of log-transformed proteinuria will be back transformed (via exponentiation) to obtain the geometric mean ratio (GMR) and corresponding 2-sided 90% CI. The values will then be expressed as percentage change in adjusted geometric mean of proteinuria at Week 26 relative to baseline.

The analysis will be performed for both proteinuria measures, UPCR and UP, in both cohorts even though the primary endpoint will be measured by UPCR for the LN cohort and by UP for the IgAN cohort.

The randomization stratification factor will be based on strata verified by laboratory and allowed concomitant therapy data from electronic case report form (eCRF). Sensitivity analysis may be performed using strata as randomized in the interactive response technology.

The data after the intercurrent events will be treated as missing, and all the missing data will be imputed according to the following assumptions:

In the LN cohort, only data up to the point of additional standard of care therapy will be included as observed for participants who receive additional standard of care therapy due to renal flare. Data on or after additional standard of care therapy for these participants is treated as missing regardless of whether the data is collected or not. The measurement performed at the time of renal flare (ie, proteinuria value from the 24-hour urine collection) will be carried forward to all subsequent visits.

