4.3.1. Secondary Endpoints

4.3.1.1. Percentage Change in Proteinuria from Baseline to Week 50 (Both Cohorts)

The percentage change from baseline in proteinuria at Week 50 will be analyzed using a mixed-effect model for repeated-measures (MMRM) using all available data up to Week 50 (either complete or partial). The data after the intercurrent events will be treated as missing. The model will include change from baseline in log-transformed proteinuria as the response variable and fixed, categorical effects of treatment sequence group, randomization stratification factor, visit, and treatment sequence group by visit interaction as well as a fixed, continuous effect of baseline log proteinuria as a covariate. An unstructured covariance matrix will be used to model the correlations among repeated measurements within each participant. If this analysis fails to

converge, a first-order autoregressive covariance matrix will be used. The Kenward-Roger approximation will be used to estimate denominator degrees of freedom.

For the LN cohort, the treatment effect will be evaluated for the ALXN2050 180 mg bid and placebo treatment groups using a contrast for treatment group-by-visit term at Week 50. The point estimate and 2-sided 90% CI for the mean difference of log-transformed proteinuria will be back-transformed (via exponentiation) to obtain the GMR and corresponding 2-sided 90% CI. The values will then be expressed as percentage change in adjusted geometric mean of proteinuria at Week 50 relative to baseline. The treatment effect will be evaluated for the ALXN2050 120 mg & 180 mg bid and placebo treatment group in the same model mentioned above.

For the IgAN cohort, participants initially randomized to the placebo treatment group will switch to receive either ALXN2050 180 mg bid or ALXN2050 120 mg bid at Week 26. Percentage change from baseline in proteinuria at Week 50 will be summarized for each treatment sequence group from the MMRM analysis and no formal treatment comparison will be made. In addition, percentage change from re-baseline (ie, Week 26) in proteinuria at Week 50 will also be summarized for each treatment sequence group descriptively.

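### The LN log-rank tests omit the corticosteroid-timing stratum; if it is prognostic they lose power, and stratifying costs almost nothing

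*SAP*

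**What the plan says.** SAP 1.2 gives the LN randomisation factor as "LN cohort: corticosteroid induction treatment initiation (prior to Screening, during Screening Period". Protocol 4.2 (Table 9) explains the choice: "A single randomization stratum was selected for each cohort to ensure equal distribution of baseline characteristics that may impact the endpoints".

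The SAP carries this factor into its models. The primary ANCOVA (SAP 4.2.2) "will adjust for baseline log proteinuria and the randomization stratification factor", using strata verified against laboratory and eCRF therapy data. The MMRM (SAP 4.3.1.1) has "fixed, categorical effects of treatment sequence group, randomization stratification factor, visit, and treatment sequence group by visit interaction". The imputation code in SAP 6.4.3 to 6.4.5 also includes it.

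The time-to-event comparisons do not. For time to spot UPCR of 0.5 g/g or less (SAP 4.3.1.6, secondary), the 180 mg and placebo curves "will be statistically compared with a log-rank test of the null hypothesis that there is no difference between the population survival curve over time". SAP 4.4.7 and 4.4.9 (exploratory) use the same sentence: "The curves for the ALXN2050 180 mg and placebo treatment groups will be statistically compared with a log-rank test". Section 4.4.7 covers two analyses, CRR alone and CRR or PRR, so four comparisons are affected. Protocol 9.4.6.2.2 likewise says only that "a log-rank test comparing the curves for ALXN2050 180 mg bid and placebo treatment groups will be performed".

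SAP 4.3 and 4.4 call these analyses descriptive, without multiplicity adjustment. No alpha, sidedness, event count or power is stated for any log-rank test.

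**The concern.** When randomisation is stratified on a factor that predicts the outcome, an analysis that ignores the factor pays in two ways. First, mixing faster and slower responders pulls the marginal hazard ratio towards 1, which lowers power however the arms are balanced. Second, if blocking has balanced the arms within strata, the unstratified log-rank variance still counts between-stratum variation that the design has removed. The test then rejects too rarely under no effect.

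There is reason to think induction timing could matter. The two strata reach Day 1 at different points of induction, and the clock for these endpoints runs while induction is lowering proteinuria: SAP 5 assumes a 40% fall on placebo by Week 26. SAP 4.6.4 plans a subgroup analysis of the primary endpoint by induction timing. With about 60 participants in the comparison there is little power to spare.

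**Working it through.** **1. The plan's own figure.** The only stated LN power is about 80% for the primary endpoint (Protocol 9.2, SAP 5). Inputs: difference ln(0.60/0.40) = 0.405, SD 0.60, 30 per arm, 10% dropout (27 evaluable), one-sided 0.05. SE = 0.60 × √(2/27) = 0.163; 0.405/0.163 − 1.645 = 0.84; power = 0.799 (0.790 with the t distribution). The stated figure is reproduced. It does not concern the log-rank tests.

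**2. The two tests compared.** At each event time j, with d events among n at risk and n₁ at risk on 180 mg:

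- U = Σ(d₁ − d·n₁/n)
- V = Σ d·(n₁/n)(1 − n₁/n)(n − d)/(n − 1)
- Unstratified: Z = U/√V over everyone.
- Stratified: Z = ΣUₖ/√ΣVₖ, with U and V computed within each stratum k.

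**3. Simulation inputs.** From the documents: 30 versus 30, the LN visit schedule to Week 50, 10% dropout. Assumed, because the documents give no value: treatment hazard ratio (HR) 2 for response, placebo response by Week 50 of 20%, 40% or 60%, stratum prevalence 50% (25% as a check), permuted blocks of six for the two arms within strata, and nominal two-sided 5%. There were 5,000 to 6,000 trials per cell; simulation error is about 0.3 points for null rates and 0.7 for power.

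**4. Results.** Each cell is unstratified / stratified, at 50% prevalence. HR 5 was run only at 40% placebo response.

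| Stratum HR | Null rate, placebo 40% | Power, placebo 20% | Power, placebo 40% | Power, placebo 60% |
|---|---|---|---|---|
| 1 | 0.048 / 0.049 | 0.263 / 0.264 | 0.475 / 0.470 | 0.595 / 0.588 |
| 1.5 | 0.047 / 0.050 | 0.269 / 0.269 | 0.457 / 0.463 | 0.582 / 0.593 |
| 2 | 0.048 / 0.056 | 0.250 / 0.257 | 0.426 / 0.449 | 0.538 / 0.578 |
| 3 | 0.039 / 0.051 | 0.245 / 0.272 | 0.385 / 0.452 | 0.473 / 0.583 |
| 5 | 0.028 / 0.051 | – | 0.317 / 0.453 | – |

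The gain from stratifying is −0.7 to +1.1 points at stratum HR 1 to 1.5, 0.7 to 4.0 points at HR 2, and 2.7 to 11.0 points at HR 3.

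**5. Checks.**

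- *Prevalence 25%, placebo 40%:* power 0.474 / 0.466 at HR 1, 0.427 / 0.447 at HR 2, 0.399 / 0.458 at HR 3. The pattern is the same.
- *No blocking within strata, HR 3, placebo 40%:* null rate 0.048 / 0.050, power 0.391 / 0.448. The conservatism goes; the power loss stays.
- *Nominal two-sided 10%, separate run of 2,500 trials per cell, placebo 40%:* power 58.2% / 57.9% at HR 1, 55.0% / 57.4% at HR 2, 51.6% / 57.5% at HR 3. With an 80:20 split of strata at HR 3: 52.6% / 57.9%.
- *Closed form:* with 30 events and HR 2, ln 2 × √(30/4) − 1.96 = −0.06, so power is 0.475, matching the simulated 0.475 at stratum HR 1 (29.7 events on average). The same formula needs 66 events for 80% power, more than the 60 participants compared.

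**The case against.** A reader might infer that these tests are conservative and underpowered as they stand. The documents do not support that. Table 9 says only that such characteristics may affect the endpoints; neither document quantifies it. The protocol also limits how far the strata can diverge: exclusion criterion 28 caps prior steroid and MMF exposure, and Protocol 6.5.3.1 brings both groups onto a common steroid schedule and MMF range early in the study. Stratum hazard ratios of 2 or 3 are therefore assumptions. Conservatism further needs balance within strata, and no block size is given. This objection stands, and it makes the consequence conditional.

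A reader might also infer that these are the only between-arm comparisons bearing on response over time. They are not: SAP 4.3.1.1 also models spot UPCR at each scheduled visit to Week 50 by an MMRM of the same kind, which includes the stratum.

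The unstratified test is a legitimate choice. It addresses the stated null of equal population curves and matches the by-arm Kaplan-Meier plots. The protocol is consistent with itself, since its ANCOVA omits the stratum too ("as the response variable and will adjust for baseline log proteinuria"); the contrast arises within the SAP. No stated decision rests on these tests, and the small event count limits them more than the missing stratum does unless the stratum is strongly prognostic. Enrolment was also paused on 06 Sep 2024 (SAP 1), so 30 versus 30 may not be reached.

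None of this is a reason to prefer the unstratified version. Being descriptive does not stop the p-values from being produced and read, and the SAP gives no reason for treating the log-rank tests differently from its other models.

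**Conclusion.** The omission is a matter of record in SAP 4.3.1.6, 4.4.7 and 4.4.9 and in Protocol 9.4.6.2.2. Its effect is conditional: power is lost if induction timing is prognostic for time to response, and the test is conservative if the arms are also balanced within strata. Under the assumptions in the working, a material loss appears only at a stratum hazard ratio of about 3 or more. Confidence is high that the stratum is missing and that stratifying is the better default; it is low on the size of the loss in this trial. The point is minor. It concerns one secondary and three exploratory comparisons, and it does not touch the powered primary analysis.

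**What to change.** In SAP 4.3.1.6, in both analyses of 4.4.7, in 4.4.9, and in Protocol 9.4.6.2.2 when next amended, specify a log-rank test stratified by corticosteroid-induction timing (before versus during Screening), using the same verified stratum variable as the ANCOVA in SAP 4.2.2. Keep the Kaplan-Meier curves and quartiles by arm. If the unstratified test is preferred, state that and give the reason.

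The cost is one STRATA term in the program. If the stratum turns out not to be prognostic, the price is at most about 1 point of power. Data collection and the primary analysis do not change.
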